7.3 Other concomitant medications

Patients must be instructed not to take any additional medications (including over-the-counter products) during the trial without prior consultation with the investigator. All medications taken within 30 days of screening should be recorded. If concomitant therapy must be added or changed, the reason and name of the drug/therapy should be recorded. In general, the use of any concomitant medication/therapies deemed necessary for the care of the patient are allowed, including drugs given prophylactically (e.g. antiemetics) with the following exceptions:

- Any medications [Appendix 1](#) which may cause QTc prolongation or inducing Torsades de pointes should not be used.
- Any medications that have the potential to alter serum electrolytes (e.g., diuretics) should be monitored very closely for electrolyte abnormalities as these can contribute to the risk of QT prolongation and ventricular arrhythmias.
- No other investigational therapy should be given to patients
- No anticancer treatments (including radiation therapy) other than the study medications administered as part of this study protocol should be given to patients. If such agents are required for a patient then the patient must first be withdrawn from the study.
- Granulocyte growth factors (e.g.G-CSF and GM-CSF) will be administered routinely to prevent and treat neutropenia.

- Concomitant use of CYP3A4 inhibitors with panobinostat should be used with caution due to a potential increase in panobinostat exposure during concomitant treatment with these drugs. Please refer to Appendix 2
- Medications known to be substrates of the isoenzyme CYP2D6 should be used with caution with panobinostat as panobinostat can inhibit isoenzyme CYP2D6 at low micromolar ranges. Please refer to [Appendix 3](#) for the list of CYP2D6 substrates. .
- Oral contraceptives are generally metabolized by CYP3A4. Since the induction potential of panobinostat to induce CYP3A4 is unknown, patients who are using oral contraceptives as a method of contraception, and are sexually active, should use another effective contraceptive method.

Anti-coagulant therapy

Panobinostat therapy is commonly associated with mild to moderate degree of thrombocytopenia. This may lead to an increase in the risk of bleeding with concomitant sodium warfarin (Coumadin®). It is recommended that patients who require anticoagulation therapy while on panobinostat therapy use low molecular weight heparin (LMWH). However, if the use of LMWH is not feasible, patients on sodium warfarin may continue such therapy while on panobinostat but for such patients, a close and frequent monitoring of the coagulation parameters, including PT/INR should be followed and they should be maintained within a therapeutic range. The dose of sodium warfarin may be adjusted as needed while on panobinostat.

8.0 CRITERIA FOR RESPONSE:

Response will be documented on tumor measurement form and/or medical record determined by PI per cheson criteria. Tumor measurements will be performed by radiologist

Response	Definition	Nodal Masses	Spleen, Liver	Bone Marrow
CR	Disappearance of all evidence of disease	(a) FDG-avid or PET positive prior to therapy; mass of any size permitted if PET negative (b) Variably FDG-avid or PET negative; regression to normal size on CT	Not palpable, nodules disappeared	Infiltrate cleared on repeat biopsy; if indeterminate by morphology, immunohistochemistry should be negative
PR	Regression of measurable disease and no new sites	≥50% decrease in SPD of up to 6 largest dominant masses; no increase in size of another nodes; (a) FDG-avid or PET positive prior to therapy; one or more PET positive at previously involved site (b) Variably FDG-avid or PET negative; regression on CT	≥50% decrease in SPD of nodules (for single nodule in greatest transverse diameter); no increase in size of liver or spleen	Irrelevant if positive prior to therapy; cell type should be specified
SD	Failure to attain CR/PR or PD	(a) FDG-avid or PET positive prior to therapy; PET positive at prior sites of disease and no new sites on CT or PET (b) Variably FDG-avid or PET negative; no change in size of previous lesions on CT		
Relapsed or PD	Any new lesion or increase by ≥ 50% of previously involved sites from nadir	Appearance of a new lesion(s) < 1.5 cm in any axis, ≥50% increase in SPD of more than one node, or ≥50% increase in longest diameter of a previously identified node >1cm in short axis. Lesions PET positive if FDG-avid lymphoma or PET positive prior to	>50% increase from nadir in the SPD of any previous lesions	New or recurrent involvement

		therapy.		
--	--	----------	--	--

Cheson et al, J Clin Oncol 2007, 25:579-586

9.1 Duration of Treatment and Patient Participation

- Patients will receive 3 cycles of ICE (phase II only) or ICE + PANOBINOSTAT (LBH589) (phase I or phase II). Responding patients who are transplant eligible will be removed from the study and offered standard of care stem cell collection regimens. Non-responding patients will be offered alternative management plan by the treating physician.

9.2 Termination of Treatment and/or Study Participation

Patients will be informed that they have the right to withdraw from the study at any time for any reason, without prejudice to their medical care. The investigator also has the right to withdraw patients from the study for any of the following reasons:

- Intercurrent illness
- Occurrence of an unacceptable adverse event
- A treatment cycle delay of ICE > 14 days
- Patient request
- Protocol violations
- Non-compliance
- Administrative reasons
- Failure to return for follow-up
- General or specific changes in the patient's condition unacceptable for further treatment in the judgment of the investigator
- Progressive disease.

At the time of withdrawal, all study procedures outlined for the End of Study visit should be completed. The primary reason for a patient's withdrawal from the study is to be recorded in the source documents.

All AEs will be followed for 30 days post last dose of study drug and recorded in database

10.0 STATISTICAL CONSIDERATION:

Phase I design:

The objective of the phase I portion is to determine the maximum tolerated dose (MTD) of Panobinostat in combination with ICE. The dose level for ICE is fixed. There are three predefined dose levels for Panobinostat.

Dose Level	Panobinostat (mg, orally) Monday-Wednesday-Friday
-1	10
0	20
1	30

The standard “3+3” design will be used for the phase I portion of the trial. Dose limiting toxicity (DLT) is defined as follows: for non-hematologic toxicities, any CTCAE v4.0 Grade 3 or greater toxicity except for grade 3 fatigue, grade 3 or 4 nausea and vomiting lasting less than 72 hours after the last dose of chemotherapy, and grade 3 non-hematologic laboratory abnormalities that resolve to grade 1 or baseline (if the patient entered the study with existing toxicity) within 14 days of the first dose of ICE chemotherapy; for hematologic toxicities using CTCAE v4.0, grade 4 neutropenia lasting greater than 14 days, grade 3 febrile neutropenia requiring antibiotics, grade 4 febrile neutropenia, and Grade 4 platelet count ($<25,000/\text{mm}^3$) at any time and lasting greater than 14 days. Applying the 3+3 design, the first cohort of 3 patients will be treated at dose level 0 and evaluated for DLT at the end of first cycle. The algorithm is as follows: (1) If 0 out of 3 patients experiences dose-limiting toxicity (DLT), the next cohort of 3 patients will be treated at the next higher dose level. (2) If 1 out of 3 patients develop a DLT, an additional 3 patients will be treated at the same dose level. If no more DLTs develop at this dose, i.e. 1 out of a total of 6 patients develops a DLT, the dose escalation continues for the next cohort of 3 patients. (3) At any given dose, if greater than 1 out of 3 patients or 1 out of 6 patients experience DLT, the dose level exceeds the MTD and 3 more patients will be treated at the next lower dose if there are less than 6 patients already treated at that dose. Following the above scheme, MTD is defined as the highest dose level in which 6 patients have been treated with less than 2 instances of DLT. Given 3 predefined dose levels, it is anticipated that up to 12 eligible patients are required for the dose-finding portion of this trial.

To better estimate the DLT rate, an expansion cohort of 10 patients will be treated at the MTD. If at any time the DLT rate exceeds 33%, then the MTD is too toxic and a lower dose than MTD will be selected for the phase II.

With the addition of Dosing Schedule B, an additional 10 patients will be treated at the MTD in a 2nd expansion cohort but at a different dosing schedule to better evaluate safety and administration of ICE.

Phase II:

The phase II part of this study is to evaluate ICE only and Panobinostat +ICE in treating patients with classical Hodgkin lymphoma. The primary outcome is complete remission (CR). The estimated accrual rate is 3 patients per month. A maximum of 70 patients will be accrued. Patients will be evaluated for response after receiving 3 doses of ICE (3 cycles). The patients will be randomized between ICE and Panobinostat + ICE arms using a Bayesian adaptive algorithm. The dose level for Panobinostat will be the dose level determined after the phase I expansion cohort. In general, the trial will proceed as follows: The initial 20 patients will be randomized fairly with probability of 0.50 each between the two arms, so that the number of patients in each arm is equal at the start of the trial. Thereafter, as the trial proceeds patients will be randomized to the two groups with unequal probabilities in favor of the treatment that, on average, yields better response rate. Consequently, each successive patient is more likely to receive the treatment with a better response rate, on average. The details of the adaptive randomization scheme are as follows:

Denote the response rate at each of the two treatment arms by $\{\pi_1, \pi_2\}$ (1 for ICE, 2 for Panobinostat+ICE). Based on the currently available data, we assume the prior distribution for the complete response rate at 3 cycles (2 months) is $\pi_i \sim \text{Beta}(0.5, 0.5)$ where $i=1, 2$. The resulting prior mean is 0.5. After the initial first 20 patients being randomized to two treatment groups with an equal probability, each new patient will be randomized to receive treatment i with probability $\rho_i = \text{prob}(\pi_i > \pi_j, j \neq i | \text{Data})$, $i, j=1,2$. If one of these two randomization probabilities falls below 0.025 then that arm will be dropped. On the other hand, if one of the two randomization probabilities exceeds 0.975 then the trial will be terminated and that treatment arm will be selected. If the trial does not stop early and the maximum 70 patients are accrued, a treatment is selected as being “better” if the probability that one treatment’s response rate is larger than the other’s response rate exceeds 0.95.

The Table below summarizes operating characteristics of the Bayesian adaptive randomization algorithm after we simulated 5,000 trials. We assume that the number of patients accrue per month is 3.

		Treatment arms	
		ICE	Panobinostat-ICE
Scenario 1:	True Prob(Complete Remission)	0.50	0.50
	Average # Patients Treated	31.2 (10, 55)	30.8 (10, 54)
	Pr(Selected)	0.117	0.122
	Pr(Selected Early)	0.0998	0.105
	Pr(Dropped Early)	0.108	0.102
	Average Length (months) to the last patient's response evaluation		23.1
Scenario 2:	True Prob(Complete Remission)	0.50	0.70
	Average # Patients Treated	19.1 (10, 45)	32.8 (10, 55)
	Pr(Selected)	0.0098	0.573
	Pr(Selected Early)	0.0096	0.49
	Pr(Dropped Early)	0.513	0.0096
	Average Length (months) to the last patient's response evaluation		18.8
Scenario 3:	True Prob(Complete Remission)	0.50	0.80
	Average # Patients Treated	14.2 (10, 31)	25.7 (10, 55)
	Pr(Selected)	0.0022	0.859
	Pr(Selected Early)	0.0022	0.781
	Pr(Dropped Early)	0.808	0.0022
	Average Length (months) to the last patient's response evaluation		14
Scenario 4:	True Prob(Complete Remission)	0.60	0.80
	Average # Patients Treated	18 (10, 42)	31.7 (10, 56)
	Pr(Selected)	0.0068	0.638
	Pr(Selected Early)	0.0068	0.556
	Pr(Dropped Early)	0.576	0.0068
	Average Length (months) to the last patient's response evaluation		17.9

The trial will be conducted using the Clinical Trial Conduct website (<https://biostatistics.mdanderson.org/ClinicalTrialConduct>) developed in University of Texas MD Anderson Cancer Center Department of Biostatistics. Through the web interface, the users can randomize patients and update last evaluation date and current patient status. When a patient is randomized, the calculations are based on all available data entered into the website. The results of the randomization are displayed to the screen for the user to view. All data will be stored in a secure SQL server database. For safety, in addition to the MDACC DSMB annual monitoring, the team including the PI, one or 2 other select investigators, and the statistician will meet at every 10 patients for the Panobinostat +ICE arm to review the toxicity data.

Analysis Plans

Patients' demographic characteristics at baseline including age, gender, and race will be analyzed, with categorical variables summarized in frequency tables while continuous variables summarized using mean (\pm s.d.) and median (range). The student t-test/Wilcoxon test will be used to compare continuous variables between different patient groups. The chi-square test or the Fisher's exact test will be applied to assess the association between two categorical variables. Complete remission rate along with its 95% CI will be estimated for each treatment arm. Logistic regression will be utilized to assess the effect of patient demographic factors and treatment on CR.

Time-to-event outcomes, including event-free survival (EFS), duration of response, and overall survival (OS), will be estimated using the Kaplan-Meier method. The log-rank test will be performed to test the difference in time-to-event distributions between patient groups. Cox proportional hazards model will be used to include multiple covariates in the time-to-event analysis.

Serum levels of TARC and biomarkers of interest such as HDAC1, HDAC2, pSTAT3, and pSTAT6 by IHC at baseline and change from baseline to post-treatment will be evaluated for each treatment arm. We will study the association between markers and CR using logistic regression models, and the association between markers and time-to-event outcomes using Cox proportional hazards models.

Toxicity data will be summarized by frequency tables. The association between both type and severity of toxicity and the treatment groups will be evaluated. No formal statistical testing will be performed on these summary data.

11.0 DATA AND PROTOCOL MANAGEMENT:

Data will be collected by a research nurse, and will be recorded in the PDMS Data Management System.

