In clinical studies, both oral and i.v. formulations of panobinostat are being explored for further development. As of 31st December 2008, twenty-two clinical studies, including clinical pharmacology, phase I and/or phase II, have either been completed or are ongoing. A total of 789 patients were enrolled, received at least one dose of panobinostat, and for whom safety data are available. These patients constitute the safety population. Most adverse events have been grade 1 or grade 2. The most common adverse events seen in the human studies concern the gastrointestinal tract (nausea, diarrhea) and the hematopoietic system (thrombocytopenia and neutropenia). Additional common toxicities have included fatigue and vomiting. With the exception of thrombocytopenia, grade 3 and 4 adverse events were uncommon. The occurrence of thrombocytopenia appears to be related to the underlying disease (incidence is higher in patients with malignancies that involved the bone marrow e.g., acute myeloid leukemia, chronic myeloid leukemia, multiple myeloma, myelodysplastic syndrome, etc.). The most common ECG findings adjudicated by central review included post-baseline increase in frequency of sinus tachycardia, T-waves changes (flat, biphasic, inverted), as well as depressed ST segment findings. The most frequently encountered laboratory abnormalities were thrombocytopenia, neutropenia, some degree of anemia and fluctuations in electrolytes, that might not be clinically relevant. Thyroid function, as monitored by the measurement of TSH and free T4, did not reveal overt hyper- or hypo- thyroidism, with fluctuations in TSH values being within normal limits. Since the dosing in this study will follow the three-times-per-week schedule, [Table 1-1](#) below, provides a summary of adverse events that occurred in >15% of the patients at any dose. [Table 0-1](#) All grade adverse events regardless of causality in patients receiving oral panobinostat three-times per week in hematologic malignancies

Primary System Organ Class PREFERRED TERM	20 mg ^a N = 103 n	30 mg ^b N = 9 n	40 mg ^c N = 14 n	60 mg ^d N = 32 n
Any primary system organ class	102(99.0)	9(100.0)	14(100.0)	29(90.6)
Blood and lymphatic system disorders	70(68.0)	6(66.7)	12(85.7)	26(81.3)
Anemia	32(31.1)	2(22.2)	2(14.3)	9(28.1)
Febrile neutropenia	9(8.7)	0(0.0)	4(28.6)	12(37.5)
Neutropenia	20(19.4)	3(33.3)	4(28.6)	7(21.9)
Thrombocytopenia	37(35.9)	5(55.6)	7(50.0)	16(50.0)

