5.1.6 Dose escalation

Standard doses of ICE chemotherapy will be used and fixed, while panobinostat doses will be escalated (Tables 5, 5.1, and 5.2). Initially, 3 patients will be treated at each dose level and will be monitored for dose limiting toxicities (DLT) for 14 days from the first dose of ICE. If no DLTs are observed in those 3 patients at the end of the observation period, escalation to the next dose level may commence. If a DLT is observed in 1 of the first 3 patients, the cohort will be expanded to a maximum of 6 patients. If 2 or more DLTs are observed in any cohort, no further escalation will take place. The maximum tolerated dose (MTD) will have been exceeded, and the preceding dose level will be recommended for the Phase-II portion of this study. If DLTs are observed in 0 dose level, -1 dose level will be evaluated for DLTs before recommending it as MTD.

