5.1.9 Non-hematologic Toxicity

For non-hematologic toxicities, DLT will be defined as any CTCAE v4.0 Grade 3 or greater toxicity except for:

- Grade 3 fatigue.
- Grade 3 or 4 nausea and vomiting lasting less than 72 hours after the last dose of chemotherapy.
- Grade 3 non-hematologic laboratory abnormalities that resolve to Grade 1 or baseline (if the patient entered the study with existing toxicity) within 14 days of the first dose of ICE chemotherapy.

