5.1.10 Hematologic Toxicity

DLT for hematologic toxicity, using CTCAE v4.0, will be defined as:

- Grade 4 neutropenia lasting greater than 14 days.
- Grade 4 febrile neutropenia.
- Grade 4 platelet count ($<25,000/\text{mm}^3$) at any time, lasting greater than 14 days.

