5.1.13 Maximum Tolerated Dose (MTD)

The MTD will be the highest dose at which no more than 1 in 6 of the patients in the cohort experiences one or more DLTs in the first treatment cycle (21 days from the first dose of panobinostat and 14 days from the first dose of ICE).

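### Section 10 counts grade 3 febrile neutropenia requiring antibiotics as a DLT and section 5.1.10 does not, so the same patients can give a different MTD

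*Combined protocol and SAP*

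**What the plan says.** Section 5.1.10 defines haematologic DLT by three items: "Grade 4 neutropenia lasting greater than 14 days", "Grade 4 febrile neutropenia", and a grade 4 platelet count that persists beyond 14 days. Section 10.0, Phase I design, restates the DLT definition just before the 3+3 algorithm. It carries the same three items and adds a fourth, in the run "grade 3 febrile neutropenia requiring antibiotics, grade 4 febrile neutropenia, and Grade 4 platelet count".

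The DLT count drives each phase I decision:

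- One DLT in the first three patients expands the cohort to six (sections 5.1.6 and 10.0).
- Section 5.1.6 stops escalation: "If 2 or more DLTs are observed in any cohort, no further escalation will take place".
- Section 5.1.13 sets the MTD: "The MTD will be the highest dose at which no more than 1 in 6 of the patients in the cohort" has a DLT. Section 10.0 gives the equivalent rule of six treated with fewer than two DLTs.
- Section 10.0 governs the expansion cohort: "If at any time the DLT rate exceeds 33%, then the MTD is too toxic".

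Sections 5 and 10.0 both take the phase II dose from the phase I result.

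**The concern.** Both lists are current, operative text, and they classify the same event in opposite ways. The event is foreseeable: section 12.0 includes neutropenic fever among the serious events expected with this therapy. That entry concerns IRB notification and does not settle whether the event is dose-limiting.

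Determining the MTD is the primary phase I objective (section 1.1). If two readers can apply the protocol correctly to the same patients and declare different doses, the objective has no single answer. The dose carried into Schedule B and phase II, and the DLT rate eventually reported, then depend on which page was consulted.

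**Working it through.** **1. Does another clause settle it?** I found none that does.

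- Section 5.1.9 has a grade 3 catch-all, but it is limited by its opening words: "For non-hematologic toxicities, DLT will be defined as any CTCAE v4.0 Grade 3 or greater toxicity except for". The adverse event table in section 3.0 places febrile neutropenia under "Blood and lymphatic system disorders", so the catch-all does not reach it.
- Section 5.1.8 gives the principal investigator discretion over grade 3 or 4 events plainly unrelated to study drug. It does not define febrile neutropenia.
- Table 7-1 has a febrile neutropenia row, but the table applies to phase II only.

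**2. The plan's own figure.** Section 10.0 expects up to 12 patients in dose finding. Under section 5.1.6, up to 6 at level 0 plus up to 6 at one other level gives 6 + 6 = 12, which matches. This figure is the same under either DLT list, so it does not show which was intended.

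**3. Same patients, two answers.** FN3 means grade 3 febrile neutropenia with antibiotics and no other DLT. The section 10.0 algorithm starts at level 0.

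| Outcomes | Section 5.1.10 list | Section 10.0 list |
|---|---|---|
| A: no events at level 0; at level 1, one FN3 in each group of three | level 0 0/3, level 1 0/3 then 0/6; MTD = level 1 | level 0 0/3, level 1 1/3 then 2/6, level 0 filled to 0/6; MTD = level 0 |
| B: two FN3 in the first three at level 0; none elsewhere | level 0 0/3, level 1 0/3 then 0/6; MTD = level 1 | level 0 2/3, level -1 0/3 then 0/6; MTD = level -1 |

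**4. How often, from this item alone.** The documents give no FN3 rate for the combination, so the rate f is an assumption. For six patients at one dose, P(X ≥ 2) = 1 − (1−f)^6 − 6f(1−f)^5:

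- f = 0.10: 1 − 0.531 − 0.354 = 0.114
- f = 0.20: 1 − 0.262 − 0.393 = 0.345
- f = 0.30: 1 − 0.118 − 0.303 = 0.580

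For the expansion cohort of 10, more than 33% means at least 4 of 10. P(X ≥ 4) = 0.013, 0.121 and 0.350 for the same rates. Under section 5.1.10 the item contributes zero to all of these.

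**5. With other DLTs present.** Assume a 10% rate of other DLTs, independent of FN3. The section 10.0 rate is then 1 − 0.90(1−f). Section 10.0 can only add DLTs, so the chance that the two lists disagree on the two-DLT limit is the difference between the two tail probabilities.

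| f | Section 10.0 DLT rate | P(≥2 of 6), 5.1.10 | P(≥2 of 6), 10.0 | Lists disagree | P(≥4 of 10), 5.1.10 | P(≥4 of 10), 10.0 |
|---|---|---|---|---|---|---|
| 0.05 | 0.145 | 0.114 | 0.212 | 0.098 | 0.013 | 0.045 |
| 0.10 | 0.190 | 0.114 | 0.320 | 0.206 | 0.013 | 0.104 |
| 0.20 | 0.280 | 0.114 | 0.536 | 0.421 | 0.013 | 0.298 |
| 0.30 | 0.370 | 0.114 | 0.717 | 0.603 | 0.013 | 0.540 |

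**6. Whole 3+3 by exact enumeration.** With assumed other-DLT rates of 5%, 10% and 15% at levels -1, 0 and 1, the probability that level 1 is declared the MTD is 0.70 under section 5.1.10. Under section 10.0 it is 0.56, 0.42, 0.20 and 0.08 for f = 0.05, 0.10, 0.20 and 0.30.

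**The case against.** The contradiction itself is not disputable. The case on the other side concerns its size and its present relevance.

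- **The event rate is unsupported.** This stands. The section 3.0 table shows all-grade, single-agent febrile neutropenia. At doses used in this trial it reports 9/103 (8.7%) at 20 mg and 0/9 at 30 mg. The higher figures, 4/14 (28.6%) and 12/32 (37.5%), are from 40 and 60 mg. Growth factor is also routine here, from day 4. The table was collected without ICE, however, so it cannot fix the combination rate in either direction. The 5% to 30% range is illustrative.
- **Six patients are not always treated.** A dose with 0/3 escalates after three. For one 3+3 pass, P(X3 ≥ 2) + P(X3 = 1)·P(X3 ≥ 1) gives 9%, 29% and 51% at f = 10%, 20% and 30%, a little below 11%, 34% and 58%. Six is nevertheless the number section 10.0 requires before an MTD can be declared.
- **The 33% rule applies at any time, not only at 10 patients.** True, but this raises the probabilities. Checked from the sixth expansion patient against a strict one-third limit, they are 4%, 21% and 47% instead of 1%, 12% and 35%. The plan gives neither a minimum number nor a denominator.
- **The MTD may already be set.** Section 2.5 reports 21 patients enrolled, and section 5.1.7 says the 10-patient Schedule A expansion was reviewed. The reported problem was thrombocytopenia; no febrile neutropenia events are described. The 33% rule is not expressly extended to Schedule B. So it is unknown whether any decision actually turned on the difference. It is equally unknown which list was used, and Schedule B treats 10 more patients at that MTD.
- **Some events count either way.** A patient who also has a qualifying grade 3 non-haematologic toxicity, such as an infection, is a DLT under both lists. The conflict affects only patients without another DLT.

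**Conclusion.** The point holds and must be fixed. Sections 5.1.10 and 10.0 give incompatible definitions of the event that determines the primary phase I endpoint, and no other text reconciles them. Two discordant patients in a cohort of six are enough to change the MTD. If the event occurs in 10% to 30% of patients and other DLTs in 10%, independently, the lists give opposite answers on the two-DLT limit in about 21% to 60% of six-patient cohorts; at a 5% event rate it is about 10%. These rates are assumptions. The existence of the conflict does not depend on them, but its practical size does. Whether any decision already taken was affected cannot be told from the documents.

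**What to change.** Reconcile sections 5.1.10 and 10.0 into one DLT list, state it in one place, and have the other section refer to it. The investigators decide which definition stands; this review takes no view.

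Then re-tally DLTs under that list for every phase I patient treated so far, including the Schedule A expansion, and record the result before confirming the MTD used for Schedule B and phase II. State in the amendment which list was applied to the decisions already made.

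The cost is amendment wording and a re-count of events already on file, since section 12.0 requires all adverse events to be documented in phase I. No new data collection or change in sample size is needed.
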